7.2 STATISTICAL ANALYSES

Treatment patterns and changes:

Treatment patterns among patients with HR+/HER2- ABC/MBC receiving Palbociclib will be analysed as the primary objective of this study. This analysis will be conducted in all patients who have received Palbociclib combination treatment. Subgroup analyses on patients who are likely to be pre-menopause might also be conducted if applicable. This analysis will be descriptive in nature and is subject to modification based on sample size and final data specifications. No statistical tests will be utilized. Continuous and categorical variables will be described using methods outlined in Section 7.1 of this document. Sankey diagrams and/or bar charts may also be used to illustrate sequencing and changes in treatment patterns if appropriate. The above-mentioned analyses will use the following or similar R packages: 'tables', 'ggplot', and 'networkD3'.

Type	Objective	Endpoint	Population	Statistical Method/Test	Covariates used	Method of adjustment for missing values	Role of the analysis related to study objectives
Table	1	Not applicable	- All patients who have received Palbociclib	Descriptive stats	Systemic therapies	Missing data will be summarized in table.	To describe treatment patterns during

PFIZER CONFIDENTIAL

			combination treatment. - Pre-menopausal patients ^a			Missing days from dates will be handled as per section 6 of this document.	study period.
Bar chart	1	Not applicable	- All patients who have received Palbociclib combination treatment. - Pre-menopausal patients ^a	Descriptive stats	Systemic therapies	Missing data will be excluded. Missing days from dates will be handled as per section 6 of this document.	To illustrate changes in treatment patterns by year.
Sankey diagram	1	Not applicable	- All patients who have received Palbociclib combination treatment. - Pre-menopausal patients ^a	Descriptive stats	Systemic therapies	Missing data will be excluded. Missing days from dates will be handled as per section 6 of this document.	To illustrate sequencing of treatments.

^a Patients who are potentially pre-menopausal may be analyzed as a subgroup for this objective. Please refer to section 4.4 of this document for further details about how this group is defined.

Pre- and Post-CDK treatment patterns:

Describing pre- and post-CDK treatment patterns and sequencing in ABC/MBC patients is one of the secondary objectives of this study. To explore treatment patterns and sequencing before the introduction of CDK4/6 inhibitor (“pre-CDK” subgroup), ABC/MBC patients diagnosed and starting systemic therapy before the introduction of Palbociclib in Canada (i.e. January 2016 to May 2016) will be investigated. To explore treatment patterns and sequencing after introduction of CDK4/6 inhibitors, a similar length of time (i.e. January – May) will be investigated; however, this will be done in 2019 to allow for sufficient time for education and uptake of CDK4/6 inhibitor usage in

PFIZER CONFIDENTIAL

[figure not shown]
clinical practice (“post-CDK” subgroup). The above dates are the time periods we propose based on clinical relevance, but they are contingent upon clinician input and review of primary objective results and are subject to change.

Treatment patterns for systemic therapy for the pre-CDK subgroup and post-CDK subgroup will be described. Sequencing of therapies received after CDK treatment will be described. Continuous and categorical variables will be described using methods outlined in Section 7.1 of this document. Bar charts may also be used to illustrate changes in treatment patterns over time if appropriate. The above-mentioned analyses will use the following or similar R packages: ‘tables’ and ‘ggplot’.

Type	Supports Protocol Objective Number	Endpoint	Population	Statistical Method/Test	Covariates used	Method of adjustment for missing values	Role of the analysis related to study objectives
Table	2	Not applicable	-Pre-CDK subgroup -Post-CDK subgroup	Descriptive stats Comparisons tests (e.g. t-test, ANOVA, Wilcoxon, Fischer)	Systemic therapies	Missing data will be summarized in table. Missing days from dates will be handled as per section 6 of this document.	To describe treatment patterns pre and post CDK.
Bar chart	2	Not applicable	-Pre-CDK subgroup -Post-CDK subgroup	Descriptive stats	Systemic therapies	Missing data will be excluded. Missing days from dates will be handled as per section 6 of this document.	To illustrate treatment patterns over time.

Time to event analysis:

PFIZER CONFIDENTIAL

CCI

Numbers

at risk and cumulative incidence will be reported for each curve. **CCI**

[REDACTED] if deemed necessary, to explore differences between variables such as clinical characteristics, baseline co-morbidities, types of treatments, lines of therapy, or 'responders' (i.e., patients who remained on treatment for 3 months or longer) and 'non-responders' (i.e., patients who remained on treatment for less than 3 months). Subgroup analyses may be conducted on pre-menopausal patients, if appropriate. Short term responders will be defined as those who are on first line therapy for up to 3 to 6 months and long term responders as those who are on first line therapy for over 6 months; the exact most appropriate definition will be defined after consulting with clinicians. The above-mentioned analyses will use the following or similar R packages: 'survminer' and 'tables'.

Type	Supports Protocol Objective Number	Endpoint	Population	Statistical Method/Test	Covariates used	Method of adjustment for missing values	Role of the analysis related to study objectives
CCI	[REDACTED]	[REDACTED]	[REDACTED]	[REDACTED]	[REDACTED]	[REDACTED]	[REDACTED]
	[REDACTED]	[REDACTED]	[REDACTED]	[REDACTED]	[REDACTED]	[REDACTED]	[REDACTED]

PFIZER CONFIDENTIAL

[figure not shown]
^a Patients who are potentially pre-menopausal are included in this subgroup. Please refer to section 4.4 of this document for further details about how this group is defined.

CCI

Type	Supports Protocol Objective Number	Endpoint	Population	Statistical Method/Test	Covariates used	Method of adjustment for missing values	Role of the analysis related to study objectives
CCI							

PFIZER CONFIDENTIAL

CCI	[REDACTED]						
-----	------------	------------	------------	------------	------------	------------	------------

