2.1 STUDY DESIGN

This study will be a retrospective chart review of structured and unstructured data from EHRs stored at Sinai Health. Pentavere's DARWENT™ technology will be trained to extract data variables from the structured and unstructured EHR data (Table 1). CCI

[REDACTED]. Once the data variables are extracted from the EHRs, descriptive analyses will be conducted.

E8 CDA
template.docx

Data extracted will include

Study population

The study period will extend from 01 January 2016 to 01 October 2021 (Figure 1). All female patients who are ≥18 years of age and are diagnosed with HR+/HER2- ABC/MBC and received a CDK4/6 inhibitor at Sinai Health during the study period will be included in the study. It is estimated that there will be approximately 300 diagnoses of MBC within the study period at Sinai Health, of which approximately 180 will be HR+/HER2-. Follow-up data from EHRs will be included up to the extent that they are available within the study period. Pre-index data (stage at initial breast cancer diagnosis, treatment being received at ABC/MBC diagnosis) may be extracted from EHRs up to 12 months before the index date.

PFIZER CONFIDENTIAL

[figure not shown]

Figure 1. Study Design Flow Chart

Data source

Patients will be selected with dates of diagnosis of HR+/HER2- ABC/MBC between 01 January 2016 and 01 July 2021. Study data will be extracted from Sinai Health EHRs up to 12 months before ABC/MBC diagnosis until the end of the study period (01 October 2021, Figure 1)

Treatment/cohort labels

1. Patients treated with Palbociclib combination treatment
2. Patients treated with CDK4/6 inhibitor.

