4 ANALYSIS SETS/POPULATIONS

4.1 FULL ANALYSIS SET

Inclusion criteria

Patients must meet all of the following inclusion criteria to be eligible for inclusion in the study:

1. *≥ 18 year old female*
2. *HR+/HER2- breast cancer diagnosis with confirmed metastatic or advanced disease*
3. *Diagnosed with ABC/MBC between 01 January 2016 and 01 July 2021*
4. *Treatment with CDK4/6 inhibitor*

Exclusion criteria

Patients meeting any of the following will not be included in the study:

1. *Patient does not have ABC/MBC*
2. *Patient has indicated HR- or HER2+ status*
3. *Patient received a CDK4/6i as part of a clinical trial*

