4.3 OTHER ANALYSIS SET

The primary objective will include only patients who received at least one dose of Palbociclib during the study period.

The secondary and **CCI** objectives will include all patients in the full analysis set.

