Age	N Mean (SD) Median Q1, Q3 Minimum-Maximum		
Sex	Female Male Unknown		
ECOG	0 1 2 3 4 Unknown		
Organ level metastatic site	Bone Brain Lungs Liver		
Number of metastatic sites	0 1 2 3 4		
Comorbidities	Atrial fibrillation Hypertension Coronary Artery Disease/Myocardial infarction/Angina Diabetes Mellitus Stroke		
Tumour stage at diagnosis	I II III IV Unknown		
Tumour grade	1		

PFIZER CONFIDENTIAL

2		
3		
Unknown		
Tumour histology		
Lobular Carcinoma		
Ductal carcinoma		
Mixed		
DCIS		
LCIS		
Other		
Unknown		
ER Receptor status		
Positive		
Negative		
Unknown		
PR Receptor status		
Positive		
Negative		
Unknown		

^a Defined as patients who were diagnosed between March 10, 2019 – March 10, 2020.

^b Defined as patients who were diagnosed between March 11, 2020-March 11, 2021.

Treatment patterns and changes:

Table 6: Line 1 Treatment Patterns in patients who received Palbociclib

Variables	Overall (N=) ^a	Pre-menopausal patients (N=) ^b
Chemotherapy N, Mean Tx duration (SD)		
Chemo drug 1, n (%)		
Chemo drug 2, n (%)		
...		
Targeted therapy N, Mean Tx duration (SD)		
Targeted drug 1, n (%)		
Targeted drug 2, n (%)		
...		
...(Any other Class of therapy observed)		

^a Includes all patients who received Palbociclib

^b Includes patients who received Palbociclib and who are potentially in pre-menopause. Please refer to section 4.4 of this document for further details about how this group is defined.

Treatment patterns and changes in patients who received Palbociclib:

[figure not shown]

Figure 1: Classes of treatments over time in patients who received Palbociclib. Similar plots will be created for all lines of therapy. Stacked bar charts can be either absolute values (as shown) or percentages, as required.

Figure 2: Sankey Diagram of treatment of patients who received Palbociclib

Treatment patterns and changes in patients who received Palbociclib who are potentially in pre-menopause.

[figure not shown]
Figure 3: Classes of treatments over time in patients who received Palbociclib who are potentially in pre-menopause. Please refer to Figure 1 for reference as to how bar charts will look. Similar plots will be created for all lines of therapy.

GER CONFIDENTIAL

Figure 4: Sankey Diagram of treatment of patients who received Palbociclib who are potentially in pre-menopause

PFIZER CONFIDENTIAL

Pre and Post-CDK treatment patterns:

Table 7: Pre and post-CDK treatment patterns and sequencing in patients

	Pre-CDK ^a			Post-CDK ^b		

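### The objective 1 by-year charts keep only patients who reach palbociclib by the cut-off, so the first-line palbociclib share rises with calendar year even if practice is constant

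*SAP*

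**What the plan says.** SAP section 7.2 lists a bar chart for objective 1 whose role is "To illustrate changes in treatment patterns by year". On the population it says: "This analysis will be conducted in all patients who have received Palbociclib combination treatment". Section 4.3 defines the set by any exposure up to the cut-off: "The primary objective will include only patients who received at least one dose of Palbociclib during the study period". No line of therapy is specified, so palbociclib at second or third line also qualifies a patient.

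The shell in SAP section 8 is Figure 1, "Classes of treatments over time in patients who received Palbociclib", and the caption adds "Similar plots will be created for all lines of therapy". A first-line chart over time is therefore planned. The caption allows counts or percentages, and the text does not define the year axis.

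Two dates set the time available to qualify. SAP section 2.1: "The study period will extend from 01 January 2016 to 01 October 2021". SAP section 4.1: "Diagnosed with ABC/MBC between 01 January 2016 and 01 July 2021". No minimum or equal follow-up is required.

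**The concern.** Membership of the chart depends on an exposure that may come after the treatment being charted, and the time allowed for it shrinks with each diagnosis year. A patient diagnosed in 2017 who starts another first-line class stays in if she reaches palbociclib within the next four to five years. A patient diagnosed in spring 2021 on the same first-line class has about six months to do so and is usually absent. Patients who start palbociclib first line are always in. The first-line mix therefore drifts towards palbociclib with no change in prescribing.

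Change over time is part of the research question (protocol section 8), and this chart is the objective 1 output assigned to it. A reader will naturally take rising bars as a change in practice. The limitations section (protocol 9.9) mentions selection and channeling bias in general terms but not this mechanism. Figure 5, the all-patient version, does not escape it, because the full analysis set itself requires a CDK4/6 inhibitor.

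**Working it through.** The plan gives no uptake figure or expected chart, so there is nothing to reproduce. A simple selection model shows direction and size.

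**Inputs from the documents**
- Cut-off 01 October 2021; diagnoses 01 January 2016 to 01 July 2021. Maximum follow-up T falls from 69.0 to 3.0 months.
- Palbociclib was not yet introduced in January to May 2016 (SAP 7.2), so first-line use is set to zero there.

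**Assumptions (not in the documents)**
- p, true first-line palbociclib share, constant from June 2016: 0.3, 0.5, 0.7.
- r, probability that a patient starting another class later gets palbociclib: 0.1, 0.3, 0.5, 0.8.
- m, median months to that later start: 9.2, 14.5, 24.8. These are median PFS values quoted in protocol section 7, used only as a rough scale.

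**Formula.** The first-line palbociclib share in the selected cohort is p / [p + (1 − p) · r · F(T)], with F(T) = 1 − 2^(−T/m).

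**By hand, p = 0.5, r = 0.5, m = 14.5**
- Diagnosed 01 July 2017: T = 51.0, F = 0.913, share = 0.5 / (0.5 + 0.25 × 0.913) = 68.7%.
- Diagnosed 01 April 2021: T = 6.0, F = 0.249, share = 0.5 / (0.5 + 0.25 × 0.249) = 88.9%.

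**Averaged over diagnosis days, p = 0.5, r = 0.5 (true share 50% throughout)**

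| m (months) | Jun–Dec 2016 | 2017 | 2018 | 2019 | 2020 | 2021 |
|---|---|---|---|---|---|---|
| 9.2 | 66.9% | 67.2% | 67.9% | 69.8% | 75.0% | 84.8% |
| 14.5 | 67.9% | 68.7% | 70.4% | 73.5% | 79.8% | 89.0% |
| 24.8 | 71.0% | 72.5% | 75.1% | 79.1% | 85.5% | 92.9% |

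**Range.** Over all 36 combinations the 2017 to 2021 change is upward. It runs from about 2 points (96.9% to 99.3%; p = 0.7, r = 0.1, m = 24.8) to about 36 points (41.4% to 77.7%; p = 0.3, r = 0.8, m = 24.8). Only r = 0 gives no trend, because the share is then 100% in every year.

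**Variations on p = 0.5, r = 0.5, m = 14.5**
- Competing death with an assumed median of 36 months: 74.4% in 2017 to 89.6% in 2021.
- True first-line use falling from 55% to 45% over 2017 to 2021: the chart still shows 72.8% rising to 86.9%.

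**Count scale.** Take 180 diagnoses spread evenly over 5.5 years, or 32.7 a year, with the same p, r and m. First-line palbociclib stays at 0.5 × 32.7 = 16.4 per full year. Other first-line classes in the cohort fall from 7.5 (2017) to 4.1 (2020) and 1.0 (half-year 2021).

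**Checks on remedies**
- Fixed 24-month window, complete follow-up only (p = 0.5, r = 0.5, m = 14.5): F = 1 − 2^(−24/14.5) = 0.683, share = 0.5 / (0.5 + 0.25 × 0.683) = 74.6% in every year from June 2016. The trend is gone, but the level is still not the true 50%.
- Line at palbociclib start, by year of start (p = 0.6, r = 1, m = 12 to 24, none before June 2016): the first-line share falls from 64.6% to 60.5% (m = 12) or 73.5% to 64.2% (m = 24) over 2017 to 2020. That is a spurious fall of 4 to 9 points. On the same inputs the planned chart rises from 61.3% to 72.4% or 66.1% to 81.2%, that is 11 to 15 points.

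**The case against.** The strongest reply is that the primary objective concerns palbociclib recipients, so a chart restricted to them describes the intended cohort truthfully. That stands: nothing in the SAP calls the chart uptake, and as a cross-section it is valid. It does not rescue a comparison between years, because each year's bar is selected with a different length of follow-up.

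Other replies stand in part. Bar charts are optional in SAP 7.2, and Table 6 and the Sankey diagram also serve the objective; but the row and shells are specified, so they should be sound if used. The caption presents counts as the displayed form, and on that scale palbociclib is not inflated; but percentages are allowed, and in counts the other classes still thin out. The amendment table expects under 30% of 180, fewer than 54 patients or about 10 per diagnosis year, so noise will be large; noise does not cancel a drift in one direction.

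A reader might go further and infer that the whole rise from 2016 is artefact, of about 23 to 26 points. That figure comes from setting 60% first-line use throughout and assuming everyone else eventually gets palbociclib with a median of 12 to 24 months (61% to 64% for 2016, 84% to 90% for 2021). The documents do not support it. Palbociclib was not available in January to May 2016, so part of any rise from that year is real, and no passage suggests universal later use.

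**Conclusion.** The concern holds for reading the objective 1 class charts as a trend. On a percentage scale the first-line palbociclib share drifts upward under constant practice, by about 2 to 36 points from 2017 to 2021. The direction follows from the inclusion rule and the dates whenever some patients first receive palbociclib after first line. The size rests on p, r and m, which are assumptions. On a count scale the effect is a loss of other first-line classes from later bars.

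A reader might also infer that the primary objective is invalid or that palbociclib counts are overstated. Neither follows. The zero first-line share before June 2016 reflects non-availability, although patients from those months appear only if they later received palbociclib. The point merits correction before the charts are produced, in proportion to a descriptive study.

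**What to change.** 1. Index the objective 1 by-year chart on calendar year of palbociclib start, and show the endocrine partner separately within each line at that start. Every patient already qualifies at that moment, so no later exposure is needed for entry.
2. Do not present line at palbociclib start by year as a trend. Diagnoses enter only from January 2016 to July 2021, so later-line starts accumulate and the first-line share drifts down.
3. If first-line class by year of diagnosis is still charted, count palbociclib only within a fixed window from diagnosis (for example 24 months) and include only diagnosis dates for which the window is complete by 01 October 2021.
4. Define the year axis. State on the chart and in the limitations that it describes palbociclib recipients and does not show uptake or change in practice. Apply the corresponding statement for CDK4/6 inhibitor recipients to Figure 5.

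Items 1 to 4 need SAP wording and data already planned for extraction. The main cost falls on item 3. A 24-month window drops diagnoses after 01 October 2019, which is 21 of the 66 diagnosis months, and also patients whose palbociclib came after the window. A shorter window keeps more years but ignores more later-line use.

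A chart with all HR+/HER2- ABC/MBC patients starting each line in each year as denominator would show true uptake. It needs patients without a CDK4/6 inhibitor, who are outside the eligibility criteria, hence a protocol amendment, ethics approval and further extraction. It is optional.

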9.2.1. Inclusion criteria

Patients must meet all of the following inclusion criteria to be eligible for inclusion in the study:

1. ≥ 18 year old female
2. HR+/HER2- breast cancer diagnosis with confirmed metastatic or advanced disease
3. Diagnosed with ABC/MBC between 01 January 2016 and 01 July 2021
4. Treatment with CDK4/6 inhibitor

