4.4 SUBGROUPS

Subgroup analyses for the primary and secondary objectives will be conducted in patients who are potentially pre-menopausal, where possible. Patients who are 50 years old or younger and are on a LHRH antagonist will be included in this subgroup. Subgroup analyses will be descriptive in nature and will depend on adequate sample size.

The secondary objective will include the following subgroups for specified analyses, where possible:

[figure not shown]
- Pre-CDK subgroup is defined as ABC/MBC patients starting systemic therapy before the introduction of CDK 4/6 inhibitor (January 2016 to May 2016).
- Post-CDK subgroup is defined as ABC/MBC patients starting systemic therapy after the introduction of CDK 4/6 inhibitor (January 2019 to May 2019).

CCI

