	Line 1	Line 2	Line 3	Line 1	Line 2	Line 3
Chemotherapy N, Mean Tx duration (SD)						
Chemo type 1, n (%)						
Chemo type 2, n (%)						
...						
Targeted therapy N, Mean Tx duration (SD)						
Targeted type 1, n (%)						
Targeted type 2, n (%)						
...						
...						

^a Defined as treatment started between January 2016-May 2016^b Defined as treatment started between January 2019- May 2019

Table 8: Sequencing of therapies after CDK 4/6 inhibitor

[figure not shown]
	Overall (N=)
Post-CDK received in L1	
Medicinal product name 1, n (%)	
Medicinal product name 2, n (%)	
...	
Post-CDK received in L2	
Medicinal product name 1, n (%)	
Medicinal product name 2, n (%)	
...	
Post-CDK received in L3	
Medicinal product name 1, n (%)	
Medicinal product name 2, n (%)	
...	

Bar charts

Figure 5: Classes of treatments over time in all patients. Please refer to Figure.1 for reference as to how bar charts will look. Similar plots will be created for all lines of therapy.

PFIZER CONFIDENTIAL

Time to event analyses in all patients:

Figure 6: TTNT1 in all patients by type of treatment

Figure 7: TTNT2 in all patients by type of treatment

Figure 8: TTC in all patients by type of treatment

Figure 9: Overall Survival in all patients by type of treatment

Table 9: Length of Line 1 treatment in short term vs long term responders

Variables	Short term responders (n=) ^a	Long term responders (n=) ^b
Chemotherapy N, Mean Tx duration (SD)		
Chemo type 1		
N		
Mean (SD)		
Median		
Q1,Q3		
Minimum-Maximum		
Chemo type 2		
N		
Mean (SD)		
Median		
Q1,Q3		
Minimum-Maximum		
...		
Targeted therapy N, Mean Tx duration (SD)		
Targeted type 1		
N		
Mean (SD)		
Median		
Q1,Q3		
Minimum-Maximum		
Targeted type 2		
N		
Mean (SD)		
Median		
Q1,Q3		
Minimum-Maximum		
...		

^a Defined as those who are on first line therapy for up to 3 to 6 months

^b Defined as those who are on first line therapy for more than 6 months

Time to event analyses in pre-menopausal patients:

Figure 10: TTNT1 in patients who are potentially in pre-menopause by type of treatment

Figure 11: TTNT2 in patients who are potentially in pre-menopause by type of treatment

Figure 12: TTC in patients who are potentially in pre-menopause by type of treatment

Figure 13: Overall Survival in patients who are potentially in pre-menopause by type of treatment

Table 10: Length of Line 1 treatment in short term vs long term responders in pre-menopausal patients^a

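### SAP Table 7 puts Lines 2 and 3 of patients who started therapy in January-May 2016 under 'Pre-CDK', although most of those lines would start after CDK4/6 inhibitor introduction

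*SAP*

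**What the plan says.** - **Purpose.** SAP 7.2 introduces the pre-CDK subgroup with the words "To explore treatment patterns and sequencing before the introduction of CDK4/6 inhibitor".
- **Subgroup definition.** SAP 4.4: "Pre-CDK subgroup is defined as ABC/MBC patients starting systemic therapy before the introduction of CDK 4/6 inhibitor (January 2016 to May 2016"). SAP 7.2 adds diagnosis to the condition: "ABC/MBC patients diagnosed and starting systemic therapy before the introduction of Palbociclib in Canada (i.e. January 2016 to May 2016) will be investigated". Both describe patients, not individual lines of therapy. The post-CDK subgroup uses January-May 2019, chosen to allow time for uptake.
- **Table shell.** SAP 8, "Table 7: Pre and post-CDK treatment patterns and sequencing in patients", has Line 1, Line 2 and Line 3 columns under both 'Pre-CDK' and 'Post-CDK'. The 'Pre-CDK' footnote reads "Defined as treatment started between January 2016-May 2016". No rule stops at introduction or flags lines that start after it.
- **Eligibility.** Protocol 9.2.1: "Diagnosed with ABC/MBC between 01 January 2016 and 01 July 2021". SAP 4.1 also requires "Treatment with CDK4/6 inhibitor", and SAP 4.3 assigns the secondary objective to the full analysis set. Protocol 9.9 says that palbociclib use before approval is not represented.
- **Follow-up.** SAP 2.1 takes data to 01 October 2021 where available.

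**The concern.** The subgroup is fixed by when a patient started treatment, but the column heading describes an era. For Line 1 the two coincide. For Lines 2 and 3 they separate as soon as a patient's next line begins after May 2016. A reader of Table 7 would take the 'Pre-CDK' Line 2 and Line 3 columns as later-line practice before CDK4/6 inhibitors existed in Canada, when they would mostly hold treatment given afterwards.

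The inclusion rule adds to this. Every 2016 starter must have had a CDK4/6 inhibitor. Where that drug was palbociclib, it was given after introduction, so it can be counted in a column headed 'Pre-CDK'.

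Table 7 is the only numeric table of treatment patterns by pre- and post-CDK era for the secondary objective. In a purely descriptive study, the labels on such a table are a large part of the result.

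**Working it through.** The documents give no share of lines before and after introduction, so there is no planned figure to reproduce. The check models when lines start.

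**Inputs**
- Window W = 5 months (January-May 2016, SAP 4.4). Eligible ABC/MBC diagnoses start on 01 January 2016, so no Line 2 or 3 can come from an earlier metastatic diagnosis.
- End of data at month 69 (01 January 2016 to 01 October 2021).
- Line 1 median m1: 10.2 or 14.5 months, the letrozole-plus-placebo PFS medians in Protocol section 7. Stress case: 3.8 months (fulvestrant plus placebo, after progression on endocrine therapy). The palbociclib-arm medians are not used for Line 1, because a pre-introduction Line 1 cannot contain palbociclib.
- Line 2 median m2: 3.8 months (fulvestrant plus placebo) or 9.2 months (palbociclib plus fulvestrant). The second is admissible because most second lines start after introduction.
- Assumptions: PFS stands in for line length, durations are exponential, Line 1 starts are uniform over the window, and there are no gaps between lines and no deaths.

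**Line 2, closed form.** With λ = ln 2 / m1,

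P(Line 2 starts by end of May 2016) = 1 − (1 − e^(−λW)) / (λW).

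- m1 = 14.5: λW = 0.2390; 1 − 0.2126/0.2390 = 0.1105.
- m1 = 10.2: λW = 0.3398; 1 − 0.2881/0.3398 = 0.1522.
- m1 = 3.8: λW = 0.9120; 1 − 0.5983/0.9120 = 0.3440.

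Dividing by the probability that Line 2 starts before month 69 (0.958, 0.989 and 1.000) gives 0.115, 0.154 and 0.344 of observed Line 2 starts inside the window.

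**Line 3.** The start time is Line 1 start + Line 1 length + Line 2 length. A simulation of 1,000,000 patients reproduced the Line 2 values and gave the Line 3 shares.

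| m1 (months) | Observed Line 2 starts after May 2016 | Observed Line 3 starts after May 2016 (m2 = 3.8 / 9.2) |
|---|---|---|
| 14.5 | about 88-89% | 97.1% / 98.6% |
| 10.2 | about 85% | 96.1% / 98.1% |
| 3.8 (stress) | about 66% | 91.0% / 95.7% |

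For even half of Line 2 starts to fall inside the window, the Line 1 median would have to be about 2.2 months or less.

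**Subgroup size.** The amendment logs expect less than 30% of 180 patients, that is, fewer than 54. With diagnoses uniform over the 66 months from 01 January 2016 to 01 July 2021 (assumption), the pre-CDK subgroup is at most about 54 × 5/66 = 4.1 patients. At the planned 180 it would be 13.6. Expected second lines inside the window at 4.1 patients are 0.1105 × 4.1 = 0.45 to 0.1522 × 4.1 = 0.62, or 0.344 × 4.1 = 1.4 in the stress case.

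**The case against.** **The footnote could be read line by line.** If each line must itself have started in January-May 2016, nothing post-introduction enters the 'Pre-CDK' columns. Table 12 supports this reading, since it uses the same three-line shell with treatments classified by their own start date. But SAP 4.4 and 7.2 define patients, and the same footnote sits on Table 4, a patient-level baseline table. On the line-level reading, Lines 2 and 3 would be nearly empty, as the arithmetic above shows. The wording is ambiguous, and neither reading gives usable pre-introduction Line 2 and 3 columns.

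**The dates may change.** SAP 7.2 says so. Moving the window does not help: diagnoses cannot precede January 2016, and the SAP places introduction at about the end of May 2016.

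**Other outputs and small numbers.** Figure 5, if produced, shows treatment classes over calendar time for all lines, and Table 8 covers sequencing after CDK4/6 inhibitors. Subgroup analyses depend on adequate sample size, and the shells may be modified. This stands and limits the consequence: the percentages may describe a handful of lines.

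**Stronger readings to avoid.** A reader might infer that almost all 'Pre-CDK' Line 2 treatment is post-introduction. That wording suits Line 3; for Line 2 'most' is as far as the inputs go. A reader might also infer that Table 7 compares two equivalent post-introduction periods, or that the change in practice must be hidden or reversed. The documents do not show this. The SAP treats 2019 as the period after uptake, and in the model most second lines of 2016 starters (about 65-75%) begin between June 2016 and December 2018, which is transitional by the SAP's own reasoning. Finally, a reader might infer that Line 1 is a clean picture of earlier practice. It is not, because criterion 4 admits only 2016 starters who later received a CDK4/6 inhibitor.

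**Conclusion.** The mismatch follows from the documents alone: a patient-level subgroup with an era label, three lines of therapy, and no cut at introduction. Followed as written, the shell places post-introduction treatment, possibly including palbociclib, under 'Pre-CDK'.

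The size rests on PFS medians as proxies for line length. Most observed Line 2 starts (about 85-89%; about 66% in the stress case) and nearly all Line 3 starts (about 96-99%; 91-96% in the stress case) fall after May 2016. Gaps between lines would raise these shares. Deaths before a late Line 2 or 3 would lower them somewhat.

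The effect is on labelling and interpretation in a descriptive table whose pre-CDK side may hold about 4 patients. No test or error rate is involved.

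**What to change.** 1. In Table 7, limit the 'Pre-CDK' versus 'Post-CDK' comparison to Line 1 started within each window.
2. Show Lines 2 and 3 in a separate sequencing block headed '2016 starters' and '2019 starters'. Do not split this block further at 31 May 2016; with the expected numbers that would give cells of 0-2 patients.
3. State in SAP 7.2 that later lines of 2016 starters are mostly post-introduction treatment and are not used to describe practice before CDK4/6 inhibitors.
4. Footnote the 2016 Line 1 column: it covers only patients who later received a CDK4/6 inhibitor (inclusion criterion 4), so it does not represent all pre-introduction practice.
5. Use the same labels on any by-line bar chart of these subgroups.

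The cost is a change to one table shell and some SAP wording. Therapy start and stop dates and line of therapy are already on the list of variables to extract, so no new data are needed. The era comparison loses its Line 2 and 3 columns, which the design cannot fill with more than a stray pre-introduction line.
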